VeraCept® Intrauterine Contraceptive (referred to as VeraCept or study drug throughout this document)

Study Design

Prospective, multi-center, single-arm, open-label, Phase 3 clinical study to 3 years with extension up to 8 years

Study Objectives

The primary objective of the study is to assess the contraceptive efficacy (prevention of pregnancy) of VeraCept.

The secondary objectives of the study are to assess the following for VeraCept:

- · Safety and tolerability
- Return to fertility after VeraCept removal, only for subjects requesting VeraCept removal to become pregnant

Study Duration

Subject enrollment will take approximately 9 months.

VeraCept subjects will be followed for up to 8 years. Women requesting VeraCept removal for a desired pregnancy will be followed for up to one year after the IUS is removed. The total study duration for a subject being followed for return to fertility could be up to 9 years. Any on-treatment pregnancies or off-treatment pregnancies with exposure to VeraCept will be followed through delivery and for at least 6 weeks post-delivery.

Number of Subjects

Approximately 1,605 subjects will be enrolled into the study to receive VeraCept on an open label basis. It is planned that approximately 1,480 of the 1,605 VeraCept subjects will be up to 35-years of age, and the remaining 125 subjects will be in the 36 to 45-year age range.

Investigational Site Information

This study will be conducted at approximately 45 centers in the US.

Follow-up

Enrolled subjects will have:

- Physical Assessments (Office Visits)
 - o Year 1: At Weeks 6, 13, 26 and 52
 - Years 2-8: Every 6 months for up to 8 years after VeraCept placement.
- Regular Follow-Up Contacts (Non-Office Visits) (e.g., via phone, email, etc.)
 - Years 1-3: Conducted monthly beginning at Week 17, except when there is a scheduled office visit, through Year 3.

Tiase 3 Cillical Investigation Fian (CIF)

Years 3-8: Additional visits will be conducted if necessary for safety issues.

Follow-up after study drug removal:

All subjects will be followed until 17-days post-IUS removal to confirm pregnancy did not occur within 7 days of VeraCept removal. All subjects will be required to use an alternative contraceptive for the first 14 days following VeraCept removal.

Follow-up for subjects desiring pregnancy:

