6.2 Potential Risks/Adverse Reactions

Evidence from prior clinical studies has demonstrated that the use of VeraCept has low rates of SAEs or AEs, and that pregnancy failure rates (intrauterine and ectopic pregnancy) have been low.

The following AEs have been reported in $\geq 2\%$ of pooled subjects in the three VeraCept studies (CMDOC-0008, CMDOC-0042, and CMDOC-0045) through 3 years of use. AEs designated with an asterisk (*) indicates AEs that were considered at least possibly related to VeraCept and/or the VeraCept placement/removal procedure in $\geq 2\%$ of pooled subjects. This list is in alphabetical order and not in order of increasing/decreasing occurrence:

- Abdominal distension
- Abdominal pain lower
- Abdominal pain upper
- Abdominal pain*
- Acne
- Anxiety
- Arthralgia
- Back pain*
- Bacterial vaginosis*
- Coital Bleeding*
- COVID-19
- Depression

- Device expulsion*
- Diarrhea
- Dizziness
- Dysmenorrhea*
- Dyspareunia*
- Fatigue
- Headache
- Heavy menstrual bleeding*
- Influenza
- Insomnia
- Intermenstrual bleeding*
- Ligament sprain
- Menometrorrhagia*
- Migraine
- Nasopharyngitis
- Nausea
- Oropharyngeal pain
- Ovarian cyst
- Pelvic discomfort*
- Pelvic pain*
- Pharyngitis streptococcal
- Post procedural discomfort*
- Post procedural hemorrhage*
- Procedural pain*
- Sinusitis
- Upper respiratory tract infection
- Urinary tract infection
- Vaccination complication
- Vaginal discharge*
- Vomiting
- Vulvovaginal mycotic infection

In addition, the following clinically significant adverse events have been reported in <2% of pooled subjects in the VeraCept studies:

- Uterine hemorrhage
- Anemia as a result of uterine hemorrhage, which may lead to the need for blood transfusion
- Ectopic pregnancy
- Ruptured ectopic pregnancy
- Increased risk of spontaneous abortion if pregnancy occurs with VeraCept in place. Remove VeraCept if pregnancy occurs.

- Pelvic infection (pelvic inflammatory disease, endometritis), which can lead to fallopian tubal damage leading to ectopic pregnancy or infertility, hysterectomy, sepsis and rarely death
- Uterine perforation, which may require laparoscopy or laparotomy to remove VeraCept from the peritoneal cavity
- Embedment, which may require additional in clinic procedures or surgical removal

There may also be risks that are unanticipated at this time. See the VeraCept Investigator's Brochure for a complete list of reported adverse events and additional information.

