- Counsel the subject that if at any time, she believes the study drug may have been expelled or is no longer in place, the subject should call immediately for an urgent study visit and refrain from having sex or use appropriate non-hormonal contraception until further evaluation is completed. (See Section 4.5 for details)
- If an IUS insertion is a failure, contact the IWRS to record the IUS insertion failure and to obtain a second IUS dispensation assignment or to discontinue the subject.

If a subject has failed two drug placement attempts, she will not be replaced.

12.4 Office Visits: Week 6 ±1Wk, 13 ±1Wk, 26 ±2Wks, and 52 ±2Wks from VeraCept Insertion

The subject will return for follow-up visits at preplanned intervals following VeraCept placement. At these follow-up visits, the following will be performed:

- Vital signs and weight
- Type(s) of menstrual products subject has used since the last visit
- Pelvic exam (string check)
- Transvaginal ultrasound to document VeraCept position, if clinically indicated
- Urine pregnancy test
- Interval and concurrent medications
- Adverse events
- Counsel the subject that if at any time, she believes the study drug may have been expelled or is no longer in place, the subject should call immediately for an urgent study visit and refrain from having sex or use appropriate non-hormonal contraception until further evaluation is completed. (See Section 4.5 for details)
- E-diary review with subject:
 - Review for completeness. If not complete, subject to enter information, if within 7- day open timeframe. Remind the subject to complete diary contemporaneously.
 - Verify sexual activity and if any back-up contraception method is documented
 - o Review subject's diary and assess for adverse events
 - o Re-education on e-diary completion, if needed

- Subject recorded adverse events
- o Subject recorded interval and concurrent medications

12.5 Regular Contact: Weeks 17, 21, 30, 34, 39, 43, 47 +1Wk and Monthly at months 13-17, 19-23, 25-29, 31-35 ±1Wk from VeraCept Insertion

Subjects will be contacted (e.g., via phone, email, etc.) starting at Week 17 from day of VeraCept insertion until Month 35 (Year 3), to review:

- Interval and concomitant medications;
- Adverse events
- Use of concomitant contraception;

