13 E-DIARIES

Subjects will be instructed to complete e-diaries daily. Training and detailed instructions on how to complete the e-diary will be provided to subjects. The screening period will be used to train the subjects on how to use the e-diary and to assess the subject's e-diary completion compliance. The diary data collected during the screening period will not be used in the analysis. Subjects will have up to 7 days to input e-diary data for each day. During subject visits and contacts, the site should review the e-diary with the subject to assess for e-diary completion. In addition, all e-diary entries should be reviewed and assessed for adverse

events and concomitant medications. Subjects should be re-educated if they are not completing the diary or are incorrectly completing it. E-diaries are designed to collect the following information for each day of the 28-day cycle from Screening through Month 12:

- Day of cycle
- Date
- Absence or presence of scheduled (menstrual) or unscheduled (intermenstrual)
 vaginal bleeding/spotting (none, spotting, light bleeding, normal bleeding or heavy
 bleeding)
- Vaginal intercourse
- IUD expulsion (yes, no, suspected)
- Usage of additional birth control methods and type of birth control used
- Presence of menstrual pain or cramping
- Adverse events
- Concomitant medications

Vaginal bleeding categories are defined as follows:

- None: no bleeding or spotting
- Spotting: a minimal amount of vaginal bleeding and only one panty liner is used all day or did not use any protection (panty liner, pad, tampon)
- Light bleeding: have vaginal bleeding and one or two pads or tampons are used, or more than one panty liner is used, throughout the day
- Medium bleeding: have vaginal bleeding and three or four pads or tampons are used throughout the day
- Heavy bleeding: have a large amount of vaginal bleeding and more than four pads or tampons are used throughout the day

From Month 13 – Month 96 the following will be collected:

- Day of cycle
- Date
- Vaginal intercourse
- IUD expulsion (yes, no, suspected)
- Usage of additional birth control methods and type of birth control used
- Adverse events
- Concomitant medications

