15.2 Definition of an Adverse Event

An adverse event is any untoward medical occurrence in a clinical investigation subject administered an investigational product and which does not necessarily have to have a causal relationship with this treatment. An AE can, therefore, be any unfavorable and unintended sign (that could include a clinically significant abnormal laboratory finding), symptom, or disease temporally associated with the use of a medicinal product, whether or not considered related to the medicinal product.

Any AE (i.e., a new event or an exacerbation of a pre-existing condition) with an onset from the day of informed consent/assent through VeraCept removal or expulsion should be recorded as an AE on the eCRF. An event that is discovered during the screening visit that clearly started or was acquired prior to obtaining informed consent (e.g., positive cervical infection test, positive cervical pathology) should be recorded as medical history and not as an AE. All AEs must be recorded regardless of the severity or relationship to study drug. It is important that investigators also report all AEs that result in expulsion or removal of the investigational product being studied, whether serious or non-serious.

Pregnancy is an outcome, and not an AE in this study.

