20.9 Determination of Sample Size

Approximately 1,605 subjects will be enrolled on an open label basis. It is planned that 1,480 of the 1,605 VeraCept subjects will be in the up to 35-year age range and the remaining 125 subjects will be in the 36 to 45-year age range. It is expected that at least 40% of enrolled subjects will be nulliparous.

It is expected that 1,480 post-menarcheal VeraCept subjects up to age 35 years will provide at least 620 women with at least 3 years of use of VeraCept. It is expected that the study will have 577 woman-years of use in Year 3 of the study who are evaluable for the Pearl Index analysis. This will allow for the Pearl Index calculation for Years 1, 2, and 3 of the study and for the cumulative 3 years to have an upper bound of the 95% confidence interval no more than 1 unit above the point estimate of the Pearl Index.

It is also expected that 1,480 post-menarcheal VeraCept subjects up to age 35 years will provide at least 350 women with 5 years of use of VeraCept.

The 1,605 enrolled VeraCept subjects are expected to provide over 17,000 cycles (28-day cycles) of exposure in Year 1. Over 54,000 VeraCept cycles are expected to be collected during the course of the 5-year study.

The 1,605 enrolled VeraCept subjects are expected to provide at least 200 women with 8 years of use of VeraCept. Over 65,000 VeraCept cycles are expected to be collected during the course of the 8-year study. These 8-year projections assume that 10% of the subjects that complete 5-years of use will not consent to extending their use of VeraCept beyond Year 5.

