4.9 Primary Endpoint Analysis

The primary efficacy endpoint is contraceptive efficacy through 3 years of use and will be analyzed using the Pearl Index with a 95% CI (CI) for women in the EP population.

The Pearl Index is defined as the number of on-treatment pregnancies per 100 women years. On-treatment pregnancy is defined as the estimated conception date being after the insertion date and no more than 7 days after the VeraCept is removed or expelled. One woman year is defined as comprising thirteen 28-day cycles.

Point estimate of Pearl Index:
$$x \times \frac{1300}{E}$$

95% CI: $\left(\frac{1}{2}\chi_{(0.025,2x)}^2 \times \frac{1300}{E}, \frac{1}{2}\chi_{(0.975,2(x+1))}^2 \times \frac{1300}{E}\right)$

where x is the number of on-treatment pregnancies and E is the number of 28-day evaluable exposure cycles and $\chi^2_{(p,df)}$ is the pth quantile of χ^2 -distribution with df degrees of freedom.

Cycles during which no intercourse occurs or backup methods of contraception (including emergency contraception) are used or there is no diary data will be excluded from the primary analysis of the Pearl Index unless the subject had an on-treatment pregnancy in that cycle. If Cycle 1 is evaluable, it will be included in the analysis regardless of the timing of VeraCept relative to the subject's last pre-insertion menses.

x =sum of PREGNANCY

E =number of Evaluable Cycles (NCYCEV)

Pearl Index point estimate and 95% CI will be calculated for Year 1, Year 2, and Year 3, separately, and for 3 years cumulatively.

The analysis will be repeated for the following subgroups

- Race (white, non-white)
- BMI group at enrollment
- Age group at enrollment
- Parity at enrollment

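### After Week 26, pregnancy tests are about six months apart and the listed contacts and visits ask no direct pregnancy question, so a pregnancy that ends between tests can go uncounted and pull the Pearl Index down by an unknown amount.

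*Protocol*

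**What the plan says.** Urine pregnancy tests fall at Weeks 6, 13, 26 and 52 (Protocol 12.4), then every six months with a window of one month either side (12.6), and at Month 96 or exit (12.7). Between them, 12.5 provides contacts "starting at Week 17 from day of VeraCept insertion until Month 35 (Year 3), to review" medications, adverse events, concomitant contraception, what to do if expulsion is suspected, and the e-diary. Table 1 schedules no pregnancy test at these contacts. They stop at Month 35. After that, the synopsis allows extra visits only for safety reasons.

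Three other passages bear on detection:

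- Section 15.2: "Pregnancy is an outcome, and not an AE in this study".
- Section 13: the list introduced by "From Month 13 – Month 96 the following will be collected" covers intercourse, expulsion, other birth control, adverse events and medications. It has no pregnancy item and no longer records bleeding.
- Section 6.2 lists, among clinically significant events reported in under 2% of pooled subjects, "Increased risk of spontaneous abortion if pregnancy occurs with VeraCept in place".

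On removal, conception up to 7 days afterwards still counts as on-treatment (Protocol 20.1). The synopsis states: "All subjects will be followed until 17-days post-IUS removal to confirm pregnancy did not occur within 7 days of VeraCept removal". The instrument is a home urine test on Day 17 with a required call (12.7). The further 30-day contact is only for adverse events still ongoing at removal or expulsion.

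**The concern.** The primary endpoint is a count of pregnancies over exposure. A pregnancy still in progress at the next visit will be found and dated. One that starts and ends between two visits meets no scheduled test, and nothing in the listed procedures asks about it directly. Section 6.2 indicates that early loss is a recognised outcome when the device is in place, so this group is not merely theoretical.

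Any under-count runs one way, in the device's favour. It would affect the Year 1 to 3 Pearl Index and, more so, the Year 4 to 8 estimates, where even the monthly contacts have ended. Section 5.2 says those later data will be used to judge whether longer use can be supported. The Kaplan-Meier estimates use the same events.

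The post-removal question is smaller: whether the Day 17 test can do what the synopsis says it does for conceptions late in the 7-day window.

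**Working it through.** **1. Spacing of tests.** From Protocol 12.4, the gaps in Year 1 are 13 − 6 = 7, 26 − 13 = 13 and 52 − 26 = 26 weeks. From Month 18 the nominal gap is 6 months. With a month either side at both visits it runs from 6 − 2 = 4 to 6 + 2 = 8 months.

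**2. What scheduled tests alone can see.** The documents do not say how long a pregnancy that ends early stays test-positive. Assume it is positive from week 2 after conception to week L, with visits on their nominal dates. In Years 2 and 3 there are two tests per 52 weeks, each covering L − 2 weeks of conception dates, so the share of conception dates with no test is 1 − 2(L − 2)/52. Year 1 uses its own four test dates.

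| L (weeks) | Year 1 | Years 2 and 3, each | Years 1–3 |
|---|---|---|---|
| 6 | 69% | 85% | 79% |
| 8 | 58% | 77% | 71% |
| 10 | 48% | 69% | 62% |
| 12 | 40% | 62% | 54% |

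These are shares of conception dates for pregnancies that end by week L. They are not shares of all pregnancies missed: an event is lost only if it also fails to surface in any other way.

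**3. Direction.** SAP 4.1.6 gives Pearl Index = 1300x/E. E is the number of evaluable cycles: relevant cycles less those with backup contraception, no intercourse or no diary data (SAP 4.1.5). A negative pregnancy test is not a condition. A counted pregnancy before removal also ends exposure at conception. If it is missed, x falls by one and E is not reduced, so the index falls.

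**4. Weight of one event in Year 3.** The plan expects that "the study will have 577 woman-years of use in Year 3 of the study" will be evaluable and aims for an "upper bound of the 95% confidence interval no more than 1 unit above the point estimate of the Pearl Index". It does not state the number of pregnancies assumed. Using the exact Poisson limit in SAP 4.9, the woman-years needed are 100 × [½χ²(0.975, 2(x+1)) − x]:

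- x = 2: 522.5
- x = 3: 100 × (8.767 − 3) = 576.7, which reproduces 577
- x = 4: 100 × (10.242 − 4) = 624.2

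At 577 woman-years:

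| Pregnancies | Pearl Index | Upper 95% limit | Distance |
|---|---|---|---|
| 3 | 0.52 | 1.52 | 0.9995 |
| 4 | 0.69 | 1.78 | 1.08 |

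One event moves the Year 3 index by 100/577 = 0.17. If three are counted and a fourth occurred, 0.52 is reported where 0.69 was true, and the one-unit target appears met when it is not.

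**5. Weight of one event in Years 6–8.** Section 20.9 gives over 54,000 cycles through Year 5 and over 65,000 through Year 8, for all ages. Taking the difference as a rough guide, (65,000 − 54,000)/13 = 846 woman-years, or 282 per year. One event then moves a yearly index by 100/282 = 0.35. The efficacy population excludes women over 35 at enrolment and non-evaluable cycles, so the true shift is probably larger.

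**6. Proportional effect.** If a fraction f of pregnancies is missed, true/observed is about 1/(1 − f): 1.05 at 5%, 1.11 at 10%, 1.25 at 20%. No document gives f, so these values are illustrative.

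**7. Day 17 test.** A conception on the day of removal is 17 days old at the test. One on Day 7 is 17 − 7 = 10 days old. No document gives the sensitivity of the home test at 10 days.

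**The case against.** The strongest reply is that a pregnancy does not have to be volunteered to be found. Section 15 makes site staff responsible for querying adverse events. Adverse events and medications are reviewed at every contact and visit, and both stay in the diary to Month 96. Pregnancy is not an adverse event, but nothing exempts a miscarriage, its bleeding and pain, or drugs taken for it. Ectopic pregnancy is a serious adverse event (15.1). This stands, and it narrows the gap to losses that leave no trace in those reviews.

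Sections 6.4 and 18 add a monthly safety and pregnancy review, immediate reporting of suspected pregnancies, urine and serum confirmation, and dating. These act on pregnancies already known or suspected; they do not prompt anyone to ask. Section 18 also points to pregnancy reporting guidelines in the Study Reference Manual, and the efficacy population requires at least one report of pregnancy status. Sites may therefore ask more than the protocol lists. The manual was not available for this review.

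A reader might go further and infer that the Pearl Index is biased low. The documents show only that it could be. A reader might also infer that denser testing in Year 1 confounds comparison between years. Detection does differ by period, but no between-year test is planned and the secondary analyses are descriptive.

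On removal, a reader might conclude that a negative Day 17 test cannot exclude a Day 7 conception and that the test should move to Day 30. The first depends on a sensitivity that the documents do not give. The second would delay detection and pick up conceptions after the 14 days of required contraception. That contraception, and the one-year follow-up of women seeking pregnancy, also make an overlooked conception less likely.

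**Conclusion.** The gap in the listed procedures is real: tests about 26 weeks apart after Week 26, and no direct pregnancy question in 12.5, 12.6 or 12.7. Any resulting error in the Pearl Index is downward. Its size cannot be derived from the documents, and the percentages above depend on an assumed test-positive period and on the event not surfacing otherwise. What can be said firmly is that the endpoint is sensitive to single events: 0.17 in Year 3, with the precision target failing at the fourth pregnancy, and roughly 0.35 in a single year of Years 6–8. That justifies a nearly free improvement. It does not justify a claim that the estimates are invalid.

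On Day 17, the stated purpose and the timing of the test do not evidently match for conceptions late in the window, and the protocol should reconcile them. Few such conceptions are to be expected.

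**What to change.** - Add one scripted question to Protocol 12.5, 12.6 and 12.7: *any positive pregnancy test, pregnancy, miscarriage or abortion since the last contact, and when?* Handle each yes under section 18 and count it by estimated conception date, with the basis for that date recorded.
- Expect the gain mainly in Years 4–8. Version 4.0 (March 2019) already responds to enrolment-period feedback, and enrolment was planned to take about 9 months. By Version 7.0 (June 2023) most women had therefore probably passed Month 35; this is an inference from the revision history.
- If the question is also asked once retrospectively, report the result as a sensitivity analysis. It reaches only women still active and relies on recall over years, so it should not be merged into the primary count.
- Reconcile the synopsis statement on Day 17 with the timing of the test, for example by keeping that test and asking about pregnancy at a later contact, or by limiting what the test is said to confirm.

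The cost is a few seconds per contact and, if events are found, a slightly higher Pearl Index. A later contact after removal would add some calls, because the present 30-day contact covers only women with ongoing adverse events.

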12.7 Month 96 +1 Month from VeraCept Insertion and/or Exit Visit

- Prior to VeraCept removal, the Pre-Removal Planning Timing guidelines (Appendix 4) must be considered to prevent unintended pregnancy after removal. It is important that VeraCept removal and the initiation of the next method of contraception occurs as per the timing guidelines. Subjects must be educated on the risks of pregnancy if the recommended guidelines are not followed (see Section 4.6).
- Vital signs and weight
- Type(s) of menstrual products subject has used since the last visit
- General physical exam
- Pelvic exam (string check)
- Transvaginal ultrasound to document VeraCept position, if clinically indicated
- Urine pregnancy test
- Interval and concurrent medications
- Adverse events
- E-diary review with subject:
 - Review for completeness. If not complete, subject to enter information, if within 7- day open timeframe.
 - o Verify sexual activity and if any back-up method is documented
 - o Review subject's diary and assess for adverse events
 - Subject recorded adverse events
 - Subject recorded interval and concurrent medications
- Subject Satisfaction Survey (only for subjects completing at least 6 years (72 months) of study)
- If a subject was unable to or unwilling to comply with the Pre-Removal Planning Timing guidelines (Appendix 4), it should be determined if the subject has had vaginal intercourse within 7 days prior to removal. If confirmed, VeraCept removal and the Exit Visit should be rescheduled. If rescheduling is not possible, emergency

contraception (EC) should be provided at time of removal if vaginal intercourse occurred within the EC effectiveness window.

- VeraCept Removal (see Appendix 5 for Removal Instructions)
 - o VeraCept removal ease
 - VeraCept removal pain. The subject completes the IUD Removal 11- Point Subject Numeric Pain Rating Scale immediately after IUS removal (see Appendix 3)
 - The IUS may be analyzed for residual copper to estimate the rate of release of copper. All removed/used devices should be retained until further instructions from Sebela. Cleaning, storage, and shipping instructions are detailed in the Study Reference Manual.
- The subject's preferred method of contraception will be provided:
 - o If the subject elects a non-hormonal method of contraception, a 14-day supply will be provided by the site
 - If the subject elects to use hormonal contraceptive pills, a one-month supply of hormonal contraceptive pills will be provided to the subject by the site for the first 14 days following VeraCept removal
 - All subjects must be provided with a 14-day supply of condoms at time of removal (unless a new IUS is inserted)
 - All subjects must be instructed to continue use of new contraception method for 14 days after removal.
- Subjects should be reminded to avoid conception within 7 days after VeraCept removal
- Contact the IWRS to update the subject status
- Urine pregnancy test will be done 17 days after removal/study exit by the subject at home, with a required follow up call by the study coordinator or PI to obtain and document results
- An additional contact will be completed 30 days after VeraCept removal for any Adverse Events that remain ongoing at the time of IUS removal or expulsion. If the date of the expulsion is unknown the additional contact will occur 30 days after the date of expulsion discovery. AE stop date and outcome are required to be updated, if applicable.

